### 6.4.5 Withdrawal Visit

Participants will be invited to complete endpoint testing even if they choose to withdraw from the intervention. Endpoint testing will include:

- BMI
- HbA1c and C-reactive protein
- MNSI symptom questionnaire and the PROMIS physical function and fatigue questionnaire
- MNSI physical exam
- VPT and Calf Muscle performance
- Plasma levels of hydrogen peroxide
- Lower leg muscle performance & physical activity

#### CONFIDENTIAL

• MRI

# 6.5 Concomitant Medications, Treatments, and Procedures

All concomitant prescription medications, over-the-counter medications, and non-prescription medications taken during study participation will be recorded on the CRF. For this protocol, a prescription medication is defined as a medication that can be prescribed only by a properly authorized/licensed clinician.

### 6.5.1 Precautionary Medications, Treatments, and Procedures

N/A

# 6.6 Prohibited Medications, Treatments, and Procedures

Oral medications such as Metformin are prohibited two full days prior to all OGTT evaluations. Participants will be asked not to take their insulin on the morning of their visit at CBI.

# 6.7 Prophylactic Medications, Treatments, and Procedures

- If hypoglycemic (less than 100 mg/dL), carbohydrate snacks will be provided and glucose testing will be repeated in 15-20 min
- No other prophylactic medications will be provided by study personnel

# 6.8 Participant Access to Study Intervention at Study Closure

Participants will be encouraged to continue exercising upon completion of the intervention as this will be beneficial to their health.

# 7 Assessment of Safety

## 7.1 Specification of Safety Parameters

## 7.1.1 Definition of Adverse Events (AE)

An *adverse event* (AE) is any symptom, sign, illness or experience that develops or worsens in severity during the course of the study. Inter-current illnesses or injuries should be regarded as adverse events. Abnormal results of diagnostic procedures are considered to be AEs if the abnormality:

- results in study withdrawal
- is associated with a serious adverse event
- is associated with clinical signs or symptoms
- leads to additional treatment or to further diagnostic tests
- is considered by the investigator to be of clinical significance

## 7.1.2 Definition of Serious Adverse Events (SAE)

#### Serious Adverse Event

Adverse events are classified as serious or non-serious. A serious adverse event (SAE) is any AE that is:

- fatal
- life-threatening
- requires or prolongs hospital stay
- · results in persistent or significant disability or incapacity
- a congenital anomaly or birth defect
- an important medical event

Important medical events are those that may not be immediately life threatening, but are clearly of major clinical significance. They may jeopardize the subject and may require intervention to prevent one of the other serious outcomes noted above. For example, drug overdose or abuse, a seizure that did not result

#### CONFIDENTIAL

This material is the property of the NYU School of Medicine and Langone Medical Center. Do not disclose or use except as authorized in writing by the study sponsor Behavioral Intervention Template Version: 5 MAY 2017

in in-patient hospitalization, or intensive treatment of bronchospasm in an emergency department would typically be considered serious.

All adverse events that do not meet any of the criteria for serious should be regarded as *non-serious adverse events*.

# 7.1.3 Definition of Unanticipated Problems (UP)

### **Unanticipated Problems Involving Risk to Subjects or Others**

Any incident, experience, or outcome that meets all of the following criteria:

- Unexpected in nature, severity, or frequency (i.e. not described in study-related documents such as the IRB-approved protocol or consent form, the investigators brochure, etc.)
- Related or possibly related to participation in the research (i.e. possibly related means there is a reasonable possibility that the incident experience, or outcome may have been caused by the procedures involved in the research)
- Suggests that the research places subjects or others at greater risk of harm (including physical, psychological, economic, or social harm).

# 7.2 Classification of an Adverse Event

### 7.2.1 Severity of Event

For AEs not included in the protocol defined grading system, the following guidelines will be used to describe severity.

- **Mild** Events require minimal or no treatment and do not interfere with the participant's daily activities.
- **Moderate** Events result in a low level of inconvenience or concern with the therapeutic measures. Moderate events may cause some interference with functioning.
- Severe Events interrupt a participant's usual daily activity and may require systemic drug therapy or other treatment. Severe events are usually potentially life-threatening or incapacitating.

## 7.2.2 Relationship to Study Intervention

The clinician's assessment of an AE's relationship to study intervention is part of the documentation process, but it is not a factor in determining what is or is not reported in the study. If there is any doubt as to whether a clinical observation is an AE, the event should be reported. All AEs must have their relationship to study intervention assessed. In a clinical trial, the study intervention must always be suspect. To help assess, the following guidelines are used.

- **Related** The AE is known to occur with the study intervention, there is a reasonable possibility that the study intervention caused the AE, or there is a temporal relationship between the study intervention and event. Reasonable possibility means that there is evidence to suggest a causal relationship between the study intervention and the AE.
- Not Related There is not a reasonable possibility that the administration of the study intervention caused the event, there is no temporal relationship between the study intervention and event onset, or an alternate etiology has been established.

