## 5.1.1 Administration of Intervention

The exercise intervention will be administered in person at NYU's Department of Physical Therapy, [name]. The site PI ([name]) and Research Associate will supervise all procedures. Health professional students may assist [name] and the Research Associate. The 10-week intervention has been previously published [24] and will include 3 days a week of moderate intensity aerobic and resistance training. Each session will last 60-90 minutes.

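### Section 7.2.2 defines Related and Not Related by overlapping lists with no precedence rule, so one adverse event can satisfy both

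*Combined protocol and SAP*

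**What the plan says.** Section 7.2.2 requires the relationship to the study intervention to be assessed for every adverse event and offers guidelines for doing so.

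- **Related** has three limbs: "The AE is known to occur with the study intervention"; a reasonable possibility of cause; "or there is a temporal relationship between the study intervention and event". The next sentence defines only the second limb: "Reasonable possibility means that there is evidence to suggest a causal relationship between the study intervention and the AE".
- **Not Related** also has three limbs: "There is not a reasonable possibility that the administration of the study intervention caused the event", or "there is no temporal relationship between the study intervention and event onset, or an alternate etiology has been established".

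The section gives no time window, no order of precedence and no intermediate category. It tells the assessor to treat the intervention as suspect, but does not frame this as a way to settle a conflict between the lists. Its sentence about doubt concerns whether an observation is an adverse event at all, not whether it is related.

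The adverse event tracking paragraph in the exercise-phase part of section 6.4 requires each event to be classed as related or unrelated to exercise. Section 7.3 lists relationship among the items recorded on the CRF. Under section 7.5 the safety officer reviews all events and evaluates cumulative safety data. Section 5.1.1 says the 10-week program "will include 3 days a week of moderate intensity aerobic and resistance training".

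**The concern.** A two-way classification works only if its categories exclude each other. Here either category can be reached through a single limb, and those limbs are not opposites. Timing alone is enough for Related, and an established other cause alone is enough for Not Related, although both can be true of the same event.

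Two hypothetical events show this. A cold caught from a family member that starts the day after a session is temporal, so Related, and has another cause, so Not Related. Calf soreness that the assessor thinks exercise may have caused, but whose onset is judged not temporal, meets Related on reasonable possibility and Not Related on timing.

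What is at stake is the consistency of the related/unrelated field. Two assessors following the text faithfully can code the same event differently. Any tabulation by relatedness would inherit that variation, and so would the safety officer's cumulative review. Section 8 sets no predefined stopping rules, so that review rests on judgement.

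**Working it through.** The plan states no figure on this point, so there is nothing to reproduce. The check has two parts.

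**1. Do the definitions exclude each other?** All inputs come from section 7.2.2. Let K = known to occur with the intervention, R = reasonable possibility of cause, T = temporal relationship, A = alternate etiology established. As written:

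- Related = K or R or T
- Not Related = (not R) or (not T) or A

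Four yes/no facts give 2 × 2 × 2 × 2 = 16 combinations.

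| Result | Condition | Combinations |
|---|---|---|
| Related only | R and T hold, A does not; K either way | 2 |
| Not Related only | none of K, R, T; A either way | 2 |
| Neither | would need R and T both absent and both present | 0 |
| Both | all the rest: 16 − 2 − 2 − 0 | 12 |

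An event with T and A present meets both definitions in all 4 of its combinations (K and R either way). A coincidentally timed event with T present but neither K nor R also meets both, whether or not another cause is established. The 16 combinations are not equally likely, and some will be rare.

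**2. How much does timing discriminate during the exercise phase?** The input is 3 sessions a week (section 5.1.1). Three assumptions are added: onset of an unrelated event is uniform over the 168-hour week, sessions fall on alternate days, and the window is one of several lengths, because the plan gives none. For windows up to 48 hours there is no overlap, so the share of the week covered is 3 × window / 168.

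| Assumed window | Calculation | Share of onsets counted as temporal |
|---|---|---|
| 12 h | 36 / 168 | 21% |
| 24 h | 72 / 168 | 43% |
| 48 h | 144 / 168 | 86% |
| 72 h | windows overlap and cover the whole week | 100% |

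On a 24 to 48 hour reading, 43% to 86% of unrelated events with random onset would be eligible for Related on timing alone. By part 1, those same events also meet Not Related.

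**The case against.** The strongest reply is that section 7.2.2 offers guidelines to a clinician, not an algorithm, and section 7.3 reserves the assessment for people qualified to make a diagnosis. A clinician faced with a cold that has an obvious source will code it Not Related, as that definition expressly allows. This has force: many overlapping cases will be settled sensibly in practice. But these are the only criteria given for a mandatory two-way call, and they do not guide when both answers fit. Nor does the instruction to hold the intervention suspect resolve it. Read as a tie-break, it would code an event with an established other cause as Related on timing, against the text of Not Related.

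The second reply is that little depends on the code, and most of this stands. Section 7.2.2 says causality does not decide what is reported, and section 7.3 captures events regardless of relationship. Section 7.4.1 sends severe events to the IRB without reference to cause. Safety is not an objective in section 2 or an endpoint in section 3.2, and section 9 plans no analysis of related events.

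A reader might also infer that the section 7.2.2 code decides whether an event is an unanticipated problem, since section 7.1.3 requires it to be "Related or possibly related to participation in the research". The documents do not support that. Section 7.1.3 explains possible relatedness by reasonable possibility of cause, does not mention timing, and does not refer to section 7.2.2. The two sections simply apply different tests, so an event could be Related under one on timing alone and fail the other.

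**Conclusion.** The contradiction holds on the text: 12 of the 16 logical combinations meet both definitions, and every event with both a temporal relationship and an established other cause is among them. For such events the required binary code is indeterminate and can vary by assessor. This is a conflict within a stated rule, not a missing detail.

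The consequence is modest. It reaches the related/unrelated coding, any tabulation built on it, and the safety officer's cumulative review. It does not reach adverse-event capture, IRB reporting of severe events, the unanticipated-problem test or the efficacy analyses.

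A reader might take 43% to 86% as the share of unrelated events that will be miscoded. The figures do not show that. They are the share of the week close to a session under assumed windows, uniform onset and alternate-day sessions. Proximity makes an event eligible for Related without forcing that code. The logical result in part 1 does not depend on these assumptions.

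**What to change.** Reword section 7.2.2 and the AE form so that both categories turn on one criterion:

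- **Related:** there is a reasonable possibility that the intervention caused the event.
- **Not Related:** there is no such possibility.
- Timing, being known to occur with the intervention, and any established alternate etiology are all weighed as evidence; none is sufficient alone.
- If doubt about the relationship remains, the event is coded Related.

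In the notation above, Related = R and Not Related = not R, so 8 of the 16 combinations fall in each category and none in both. Being known to occur should not stay as a separate sufficient limb. An event of a kind known with exercise but fully explained by something else (K present, R absent) would still meet both definitions.

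The cost is a few sentences in the protocol and a change to the form, with no new data or visits. The small downside is that the assessor must make a causal judgement where timing alone used to suffice; the doubt rule keeps the coding conservative.

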## 7.2.3 Expectedness

[name], the study's safety officer, will be responsible for determining whether an AE is expected or unexpected. An AE will be considered unexpected if the nature, severity, or frequency of the event is not consistent with the risk information previously described for the study intervention.

Adverse events will be collected at each study visit by the technologist performing the MRI scan.

# 7.3 Time Period and Frequency for Event Assessment and Follow-Up

The occurrence of an AE or SAE may come to the attention of study personnel during study visits and interviews of a study participant presenting for medical care. All AEs including local and systemic reactions not meeting the criteria for SAEs will be captured on the appropriate CRF. Information to be collected includes event description, date of onset, clinician's assessment of severity, relationship to study intervention (assessed only by those with the training and authority to make a diagnosis), and date of resolution/stabilization of the event. All AEs occurring while on study must be documented appropriately regardless of relationship. All AEs will be followed to adequate resolution.

Any medical condition that is present at the time that the participant is screened will be considered as baseline and not reported as an AE. However, if the study participant's condition deteriorates at any time during the study, it will be recorded as an AE. UPs will be recorded in the data collection system throughout the study.

Changes in the severity of an AE will be documented to allow an assessment of the duration of the event at each level of severity to be performed. AEs characterized as intermittent require documentation of onset and duration of each episode.

The PI/research coordinator will record all reportable events with start dates occurring any time after informed consent is obtained until 7 (for non-serious AEs) or 30 days (for SAEs) after the last day of study participation. At each study visit, the investigator will inquire about the occurrence of AE/SAEs since the last visit.

All unresolved adverse events should be followed by the investigator until the events are resolved, the subject is lost to follow-up, or the adverse event is otherwise explained. At the last scheduled visit, the investigator should instruct each subject to report any subsequent event(s) that the subject, or the subject's personal physician, believes might reasonably be related to participation in this study. The investigator should notify the study sponsor of any death or adverse event occurring at any time after a subject has discontinued or terminated study participation that may reasonably be related to this study.

# 7.4 Reporting Procedures – Notifying the IRB

# 7.4.1 Adverse Event Reporting

Severe AEs will be reported to the IRB within 5 working days. Other adverse events will not be reported to the IRB.

# 7.4.2 Unanticipated Problem Reporting

Incidents or events that meet the OHRP criteria for UPs require the creation and completion of an UP report form. It is the site investigator's responsibility to report UPs to their IRB and to the NIH. The UP report will include the following information:

- Protocol identifying information: protocol title and number, PI's name, and the IRB project number;
- A detailed description of the event, incident, experience, or outcome;
- An explanation of the basis for determining that the event, incident, experience, or outcome represents an UP;
- A description of any changes to the protocol or other corrective actions that have been taken or are proposed in response to the UP.

To satisfy the requirement for prompt reporting, UPs will be reported using the following timeline:

- UPs that are SAEs will be reported to the IRB and to the NIH within 24 hours of the investigator becoming aware of the event.
- Any other UP will be reported to the IRB and to the NIH within 5 working days of the investigator becoming aware of the problem.

#### CONFIDENTIAL

• All UPs should be reported to appropriate institutional officials (as required by an institution's written reporting procedures), the supporting agency head (or designee), and OHRP within 5 working days of the IR's receipt of the report of the problem from the investigator.

# 7.4.3 Reporting of Pregnancy

Should a participant get pregnant during the course of the study, he/she will be discontinued immediately. The pregnancy will be documented and reported to the IRB.

# 7.5 Safety Oversight

Safety oversight will be under the direction of the safety officer, [name]. [name] study responsibilities include the following:

1) Review all AEs/SAEs on a regular basis throughout the trial

2) Be available to advise the investigators on trial-related medical questions or problems

3) Evaluate cumulative participant safety data and make recommendations regarding the safe continuation of the study.

# 8 Data Safety Monitoring Plan

Meetings among members of the research team will be held quarterly to discuss the preliminary report and to ensure that the study is being conducted according to the protocol. Additionally, members will discuss whether any protocol amendments are necessary and whether the safety/privacy of subjects who are participating is being respected. The following events/data points will be reviewed:

- Subject attrition
- Occurrence of adverse events
- Subject compliance
- Subject complaints
- Site issues (i.e. scheduling, recruiting, staffing, study flow, etc.)

There are no predefined stopping rules for the entire study.

## Responsibilities and roles for gathering, evaluating and monitoring the data:

- PI will gather data regarding recruitment rate. This will be reviewed with members of the research team every month.
- PI and co-investigators overseeing the MRI scan will gather data regarding unanticipated adverse events. The PI and co-investigators will report any serious adverse event immediately to the NYU IRB.

### Assessments:

• The PI and Co-PI will assess the risk to benefit ratio and determine whether the level of risk and patient safety were accurately outlined and accounted for in study application, protocol and consent. These meetings will occur annually when the study is being prepared for re-approval. The IRB will be informed if any reasons warrant "holding" the study.

## Procedures for Communicating – Dissemination of safety information

As appropriate:

• The PI will notify in writing the outcomes of the monitoring events. Any significant deviation will be reported immediately to the IRB using the IRB Reportable New Information form of Research Navigator.

#### CONFIDENTIAL

 New information that would affect the safety of the subject or his/her decision to participate in the study will be provided by the PI or his co-investigators.

# 9 Statistical Considerations

# 9.1 Statistical and Analytical Plans

The primary objective is to assess and compare the interventions (exercise versus control phase in the same individual) in terms of the baseline to follow-up change in the following outcomes: 1) DTI, plasma ROS level, and the MNSI assessment of DPN symptoms (Aim 1); and 2) leg mitochondrial function, oxidative capacity (31P-MRI), peak MV response (BOLD-MRI), the proportion of fat-free muscle (IDEAL-MRI) and leg muscle strength (Aim 2).

# 9.2 Statistical Hypotheses

**Hypothesis 1a:** Exercise will improve peripheral nerve integrity (DTI fractional anisotropy will increase, and the apparent diffusion coefficient will decrease).

Hypothesis 1b: Exercise will decrease plasma ROS levels.

Hypothesis 1c: Exercise will improve DPN symptoms, assessed with the MNSI.

**Hypothesis 2a:** Exercise will increase leg mitochondrial function, as defined by an increase in oxidative capacity (measured using P-MRI).

**Hypothesis 2b:** Exercise will improve leg MV function, as defined by an increase in peak MV response (measured using BOLD-MRI).

**Hypothesis 2c:** Exercise will decrease intramuscular fat and increase levels of fat-free muscle (measured using IDEAL-MRI).

# 9.3 Description of Statistical Methods

A weighted paired sample *t*-test will be used to assess whether each outcome changed from baseline to follow-up as a result of the exercise intervention. Weighted analysis of covariance (ANCOVA) will be used to compare the time points in terms of the change in each outcome. The change in each outcome from baseline to follow-up will be the dependent variable and the ANCOVA model will include the matching factors (age, baseline MNSI) and the measure of general activity level as numeric covariates and the binary indicator of intervention as a classification factor. The secondary objective is to assess the extent to which exercise induced improvements in DTI outcomes are mediated or explained by reduction in ROS. After testing the effect of the intervention on the change in DTI and the correlation between changes in DTI and ROS, an incomplete causal pathway meditational analysis will be conducted using the method of Baron and Kenny[63] with a bootstrap based test of the indirect (mediation) effect of ROS. The exploratory objective to identify baseline factors (e.g., age, MNSI, general activity) predictive of improvement, represented as the baseline to follow-up change in each outcome, will be addressed using linear regression and bivariate correlations. This analysis will be stratified by intervention and then conducted using data from both intervention groups combined. In each case, the assessment of compliance will be included as a weighting factor.

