# **Protocol Summary**

Title	A cross-over, single-center study investigating the effects of exercise on reversing diabetic peripheral neuropathy
Short Title	Reversing diabetic peripheral neuropathy through exercise
Brief Summary	This project proposes a longitudinal design that uses multinuclear-MRI to evaluate the mechanistic effects of exercise on skeletal muscle function and peripheral nerve integrity in patients with diabetic peripheral neuropathy (DPN), and to determine whether exercise can reverse DPN symptoms. We will prescribe a 10-week exercise program to 40 DPN patients. We will acquire multinuclear-MRI data before and after the intervention that can provide mechanistic insight into the adaptations in lower leg muscle function and peripheral nerve integrity of patients with DPN, and their role in improving DPN symptoms following physical exercise intervention.
Phase	N/A
Objectives	Objective 1: Determine the effect of exercise on peripheral nerve architecture, function, and symptoms of DPN. Objective 2: Determine the effect of exercise on lower leg muscle structure and function in DPN patients.
Methodology	Longitudinal design
Endpoint	Body mass index (BMI), glycosylated hemoglobin (HbA1c), and C-reactive protein will be assessed before and after the 10-week intervention, along with the following measures of neuropathic symptoms: 1) Michigan Neuropathy Screening Instrument (MNSI) symptom questionnaire and the PROMIS physical function and fatigue questionnaire, 2) MNSI physical exam score, 3) Vibration Perception Threshold (VPT) and Calf Muscle performance, 4) Plasma levels hydrogen peroxide as marker of ROS, 5) Lower leg muscle performance (9-item Physical Performance Test), activity monitor with actigraph, and 6) Multinuclear MRI will assess changes in muscle function and peripheral nerve integrity. 7) Utah Early Neuropathy Scale, which is a physical exam specific to early sensory predominant polyneuropathy.
Study Duration	2 years
Participant Duration	~10 weeks
Duration of behavioral intervention	10 weeks
Population	40 patients with Type 2 diabetes and clinical symptoms of DPN (both male and female) between the ages of 40-70 years old
Study Sites	Single-center
Number of participants	40 participants expected to be enrolled across one site

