# 2 Objectives and Purpose

# 2.1 Primary Objective

The primary objective is to assess and compare the interventions (exercise versus control phase) in terms of the baseline to follow-up change in the following outcomes: 1) DTI, plasma ROS level, and the MNSI assessment of DPN symptoms (Aim 1); and 2) leg mitochondrial function, oxidative capacity (31P-MRI), peak MV response (BOLD-MRI), the proportion of fat-free muscle (IDEAL-MRI) and leg muscle strength (Aim 2).

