# 9.3.2 Analysis of the Primary Efficacy Endpoint(s)

A matched-pairs Wilcoxon signed rank test will be applied to the within-subject change in each outcome among subjects demonstrating full compliance with the exercise program. Additionally, weighted analysis of covariance (ANCOVA) will be used to test the change in each outcome adjusting for the measured level of compliance using data from all subjects. The values of each outcome at

CONFIDENTIAL

baseline and follow-up for all subjects will be the dependent variable and the ANCOVA model will include time (baseline versus follow-up) as the within-subject factor of interest covariates, the measure of compliance as numeric covariate and an anonymized subject ID as a classification factor so that the comparison of times will be based on their within-subject difference. The secondary objective is to assess the extent to which exercise induced improvements in DTI outcomes are can be at least partially explained by reduction in ROS will be addressed using linear regression, The baseline to follow-up change in each outcome will be the dependent variable and the model will include the measure of compliance as a numeric factor and the within-subject change in ROS as the numeric factor of interest. A second regression will be conducted with baseline factors (e.g., age, MNSI, general activity) added to the model in order to identify factors predictive of improvement in each outcome.

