### 9.3.4 Adherence and Retention Analyses

The analysis will follow the intention-to-treat (ITT) principle and include data from every subject irrespective of whether the subject was compliant with the assigned intervention. A quantitative assessment of compliance with the intervention, ranging from 0 (complete non-compliance) to 1 (full compliance), will be included as a weighting factor to allow more compliant subjects to contribute more to the analysis. The weight for the control phase will be set to 1 since subjects are not required to exercise.

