### 9.3.6 Exploratory Analyses

The exploratory objective to identify baseline factors (e.g., age, MNSI, general activity) predictive of improvement, represented as the baseline to follow-up change in each outcome, will be addressed using linear regression and bivariate correlations. This analysis will be stratified by intervention and then conducted using data from both phases combined. In each case, the assessment of compliance will be included as a weighting factor

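### The only model that compares exercise with the control phase has no subject term, and the documents disagree on whether a control-phase MRI change will exist

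*Combined protocol and SAP*

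**What the plan says.** Section 2.1 states: "The primary objective is to assess and compare the interventions (exercise versus control phase) in terms of the baseline to follow-up change". Section 9.1 repeats this and adds "exercise versus control phase in the same individual". The title reads "A cross-over, single-center study investigating the effects of exercise on reversing diabetic peripheral neuropathy". Section 9.3.4 treats control-phase data as part of the analysis: "The weight for the control phase will be set to 1 since subjects are not required to exercise".

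The analysis sections do not carry this through consistently.

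- **Section 9.3.** A weighted paired t-test examines change from baseline to follow-up. A weighted ANCOVA on change scores then includes age and baseline MNSI, described as matching factors, together with "the measure of general activity level as numeric covariates and the binary indicator of intervention as a classification factor". No subject identifier or random effect is listed. The exploratory analysis is stratified by intervention, "then conducted using data from both intervention groups combined".
- **Section 9.3.6.** The parallel sentence refers to phases: "This analysis will be stratified by intervention and then conducted using data from both phases combined".
- **Section 9.3.2.** A second ANCOVA does include a subject identifier, "so that the comparison of times will be based on their within-subject difference". Its factor is time (baseline versus follow-up), not phase.
- **Section 9.3.5.** No comparison between groups is planned.

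On scans, sections 1.2 and 3.1 and Attachment A give three (Attachment A: weeks 1, 5 and 18). Sections 9.3.1 and 12.3 give two. Section 6.4.4 compares the final MRI with results from before the intervention, which fits either the enrolment scan or the pre-intervention scan.

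**The concern.** If three scans are done, each of 40 people supplies a control-phase change and an exercise-phase change, and the section 9.3 model receives 80 rows. Without a subject term it takes the variance of the phase difference to be the sum of the two variances. That is right only if the two changes are uncorrelated. They share a scan, so there is no reason to expect this. If the exercise change starts at visit 2, visit 2 enters the two changes with opposite signs, which pushes their correlation down. If both start at visit 1, that scan enters both with the same sign, which pushes it up. The p-value and interval for the stated primary comparison would then be wrong, in a direction set by a choice the plan does not state. If only two scans are done, the comparison cannot be made on MRI outcomes.

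**Working it through.** **Inputs.** From section 9.4: n = 40, two-sided 5%, within-subject correlation 0.5 for one pair of measures, and Table 4 change SDs (BOLD 1.26 exercise, 1.42 control; PCr 12.85 and 8.53) and means (BOLD 1.11 and 0.18; PCr 10.61 and 0.06). No three-visit covariance is given, so every structure below is an assumption.

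**The plan's own figures.** The minimum detectable within-subject change, 2.80 × SD/√40, is 17.2% (BOLD), 13.8% (PCr) and 15.2% (MNSI) of the baseline mean, inside the stated 10% to 18%. For the phase difference, the plan's 5.2 and 176 match 0.93/0.18 = 5.17 and 10.55/0.06 = 175.8, so its figures are multiples of the control change. With independent phases, 2.80 × √(1.26² + 1.42²)/√40 = 0.841, or 4.67 times 0.18 (stated 4.5). For PCr, 6.83/0.06 = 113.9 (stated 120). The match is approximate and close to what rounding of the control means allows. It suggests that the power text also treats the phases as independent.

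**Size of the section 9.3 test.** Let C and E be the control and exercise changes, and V = Var(E − C)/[Var(E) + Var(C)]. The model assumes V = 1. Actual size = 2 × [1 − Φ(1.96/√V)].

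*Exercise change from visit 2, no person-specific trends.* With equal correlations ρ and unit variances, Var(C) = Var(E) = 2(1 − ρ) and Cov = −(1 − ρ). So r = −0.5, V = 1.5 and size = 11.0% for any ρ.

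| Assumed structure | r | V | Size |
|---|---|---|---|
| Equal correlations | −0.50 | 1.50 | 11.0% |
| AR(1), 0.5 per visit | −0.25 | 1.25 | 8.0% |
| Decay over weeks 1/5/18, 0.5 per 13 weeks | −0.155 | 1.139 | 6.6% |
| Same, 0.8 | −0.058 | 1.050 | 5.6% |
| Same, 0.9 | −0.028 | 1.024 | 5.3% |

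*Adding person-specific linear trends.* Take decay 0.8 with slope SD 0.3 per 13 weeks. The trend adds 0.09 × (4/13)² = 0.0085 to Var(C), 0.09 to Var(E) and 0.09 × 4/13 = 0.0277 to the covariance. Var(C) becomes 0.1412, Var(E) 0.490 and Cov +0.0144. V = 1 − 0.0288/0.6312 = 0.954, and size is 4.5%. The same slope SD gives 6.1% with decay 0.5 and 3.5% with decay 0.9. Slope SD 0.8 gives 3.9%, 1.9% and 1.1% for decay 0.5, 0.8 and 0.9. So 5.3% is not a floor.

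*Both changes from visit 1.* Equal correlations: r = +0.5, V = 0.50, size 0.6%. AR(1): 0.1% to 0.2%. Decay: V = 0.62 to 0.63, size 1.3% to 1.4%. The phase contrast is then (v3 − v1) − (v2 − v1) = v3 − v2.

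**Power at the anticipated BOLD difference, 1.11 − 0.18 = 0.93.** In the visit-1 case the unpaired model uses a standard error of 1.898/√40 = 0.300. The true value is 0.227 at r = 0.43 and 0.174 at r = 0.67. Power is Φ[(0.93 − 1.99 × 0.300)/0.227] = 93% and, with 0.174, 97%.

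For a paired contrast, SD = √(1.26² + 1.42² − 2r × 1.26 × 1.42), with noncentral t on 39 df:

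| r | SD | BOLD power |
|---|---|---|
| 0 | 1.90 | 85.6% |
| −0.155 | 2.04 | 80.3% |
| −0.25 | 2.12 | 77.2% |
| −0.5 | 2.32 | 69.5% |

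PCr power runs from 98.8% (r = 0) to 93.7% (r = −0.5).

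**The case against.** The strongest reply is that section 9.3.2, which is headed as the primary efficacy analysis, is already within-subject. Read with the two scans in sections 9.3.1 and 12.3 and the absence of group comparisons in section 9.3.5, it forms a coherent pre-post plan. On that reading the section 9.3 ANCOVA is leftover text from a two-group design, where no subject term would be needed. The wording about matching factors and intervention groups supports this.

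Much of this stands. The pre-post tests are sound on this point, and the error rates apply only if three scans are done and section 9.3 is run literally. But sections 2.1, 9.1, 9.3.4 and 9.3.6 still promise and weight a control phase, and no other model tests it. The reply explains how the conflict may have arisen; it does not remove it.

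A reader might infer that the phase test is anti-conservative, with error up to 11%. The documents do not support that as a general statement. The 11% needs equal correlations across gaps of 4 and 13 weeks, section 9.4 itself expects correlations above 0.5, and modest individual trends take the size below 5%. A reader might also infer a serious loss of power if both changes start at visit 1. At the difference the plan anticipates for BOLD, unpaired power is still 93% to 97%.

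**Conclusion.** The comparison named as primary has no valid model. The one model with an intervention term omits the subject, and the within-subject tests answer a different question. With two scans the comparison cannot be run on MRI outcomes. With three, the section 9.3 test has the wrong variance whenever the two changes are correlated. Confidence in the missing term and the scan conflict is high, because both are in the text.

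Confidence in the size of the error is medium to low. With a visit-2 start even the direction is not established; with a visit-1 start the test is conservative under every structure examined. It does not follow that the trial's baseline-to-follow-up results would be invalid, or that the study is underpowered: the plan's claim of more than 80% BOLD power holds for a paired contrast if r is above about −0.16. This should be fixed before analysis.

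**What to change.** 1. Reconcile the number of scans across sections 1.2, 3.1, 9.3.1, 12.3 and Attachment A, and state which scan starts the exercise-phase change.
2. If the phase comparison is kept, replace the section 9.3 ANCOVA with a within-subject contrast: a paired test of each person's difference between the two changes, subject as a fixed factor, or a three-visit repeated-measures model with unstructured covariance. A random intercept on the two changes is not enough, because it cannot represent negative correlation (in simulation it still rejected 6.0% to 10.8%). Use one compliance weight per person or none, and the same subject term where section 9.3.6 pools phases. If both changes start at visit 1, say that the contrast is v3 − v2, a pre-post test.
3. If only two scans are done, restate the primary MRI comparison as pre-post and drop the claim of a control-phase comparison.
4. Remove the two-group wording in section 9.3, or reconcile it with sections 9.3.5 and 9.3.6.
5. State that the contrast assumes no drift over phases of unequal length (4 weeks versus at least 10).
6. In section 9.4, state that more than 80% BOLD power for the paired contrast needs r above about −0.16, while PCr stays above 90%.

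The cost is wording, with no new measurements if three scans are done. If the two changes are negatively correlated, intervals for the phase contrast widen by up to about 22% (√1.5 = 1.22), and BOLD power falls to 69.5% at r = −0.5.
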